A Randomized Controlled Trial Comparing Retropubic KIM sling to TVT Exact Midurethral Sling

NCT number: NCT04985799

Document Date: April 15, 2021

A Randomized Controlled Trial Comparing Retropubic KIM sling to TVT Exact Midurethral Sling

BACKGROUND / RATIONALE

Midurethral slings (MUS) are recognized as a minimally invasive treatment of stress urinary incontinence (SUI). The retropubic route of MUS placement has a cure rate of 89.1%¹ with long term subjective cure rates ranging from 51-88%.² The Neomedic Knotless Incontinence Mesh (KIM) sling is a tension-free macroporous monofilament polypropylene knotless mesh designed to be resistant to elongation and deformation over time.³ The KIM sling also offers a reusable trocar, which results in less waste and cost- savings. KIM sling trocars are available for the retropubic route or trans-obturator (TOT) route.

While studies have been performed comparing the TOT approach of the KIM sling to other slings, no studies have been performed to date with the retropubic (RP) approach. The RP and TOT approaches to MUS have been shown to be equivalent in the treatment of SUI.⁴ Since the same mesh material of the KIM sling is used for both the TOT and RP approach, we can conclude that the RP route would show similar treatment success rates.

A type 1 macroporous (> 75um) polypropylene mesh is the most appropriate material for vaginal implantation.⁵ Currently in our practice we use the Gynecare TVT Exact sling, which meets these requirements. However, Chapple et al suggest that the design and weave of synthetic mesh material can also have a significant effect on efficacy and safety;⁵ therefore, the novel design of the KIM may be beneficial to reduce complications. If we can show there is similar efficacy with the RP approach of the KIM sling to the TVT Exact, there will be benefit of reduced costs and the potential for less complications. With this study, our aim is to show non-inferiority of the KIM sling to the Gynecare TVT Exact.

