Participating surgeons will undergo training on how to place KIM sling. This includes but is not limited to teaching or device representatives in the operating room for intraoperative questions. These surgeons already have experience in placing Gynecare TVT Exact slings, as this is the current standard of care. The KIM sling has subtle differences in placement which will be addressed at the training. All surgeons in the study will undergo one training together prior to the start of the study and will have individual help from device representatives.

Randomization, Concealment, and Blinding

The randomization schema will be created using Stata, and this schema will be uploaded into the REDCap database, where randomization will be performed and maintained. This technique will be used to prevent selection bias by concealing the allocations from those assigning participants until the moment of assignment. Randomization will occur in the operating room prior to performing the procedure. Assignment codes will remain within REDCap with access to the randomization for the research investigators. The randomization codes will not be broken unless knowing the sling type affects

the patient's health or if there is a complication postoperatively that requires knowing the type of sling placed.

Masking (Blinding)

This study will be double blinded. While the providers in the operating room placing the sling will not be able to be blinded, the subjects and data collectors will be blinded to the treatment assignment.

Study Procedures and Schedule

Procedures	Screening	Baseline	Intervention	6 weeks visit	6 month visit	1 year visit
Eligibility Assessment	Х					
Informed Consent		Х				
Medical History		Х				
Study Intervention			Х			
PFDI-20		Х		Х	Х	Х
PGI-I				Х	Х	Х
Symptom Questionnaire				Х	Х	Х
Physical Exam				Х		Х

Screening (within 6 months prior to enrollment)

Pre-screening will be performed through a provider visit, obtaining history, physical exam and urodynamics study if needed, where the patient will be evaluated for if they are eligible for a sling. If the patient is deemed eligible, they will verbally be consented to be screened for and contacted regarding the research study. The research coordinator will screen for eligibility and will contact the patient to further discuss the study. This screening will take place within 6 months prior to enrollment.

Enrollment / Baseline (Day 0)

- Informed consent
- PDFI-20

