- Obtain baseline characteristics (medical history)

Visit 1 (Surgical intervention- within 6 months of enrollment)

• Intervention- randomized to treatment

Visit 2 (6 ± 2 weeks from intervention)

- PFDI-20
- PGI-I
- Symptom questionnaire
- Physical exam
- Adverse event / SAE assessment

Visit 3- phone (6 ± 2 months)

- PFDI-20
- PGI-I
- Symptom questionnaire

• Adverse event / SAE assessment

Final Visit (1 year ± 2 months)

- PFDI-20
- PGI-I
- Symptom questionnaire
- Physical exam
- Adverse event / SAE assessment

Statistical Analysis Plan

Strategies that Apply to all the Specific Aims

- To help ensure replicability of the research, the analysis plans will be reviewed and finalized prior to collection of data (a priori). For each specific aim, the analysis plans specify detailed steps for obtaining estimates of population parameters (e.g., treatment effects) and for making inferences.
- Descriptive graphical and tabular methods will be used to characterize the participants, visualize the data and examine relationships among variables.
- For each specific aim, the analyses will focus on the magnitude and direction of point- and interval-estimates of the population parameters of interest. To indicate precision, all statistical estimates of population parameters will be tabulated along with corresponding confidence intervals (CI) or standard errors (SE). The CI will be interpreted as the set of potential values of the population parameter that are most compatible with the observed data.
- All hypothesis tests yielding p-values that are deemed to be not statistically significant will be reported as being inconclusive. The proposed statistical analysis strategy acknowledges that no p-value can reveal the plausibility, presence, truth, or importance of an association or effect.

Plans for Aim 1:

To assess the non-inferiority in the effectiveness of the retropubic Neomedic KIM sling compared to Gynecare TVT Exact sling at 6 weeks, we will present the 2-by-2 contingency tables on SUI treatment success counts. Then, we will perform the one-sided hypothesis test of H_0 : (PTVT – PKIM) > Δ vs H_a : (PTVT – PKIM) $\leq \Delta$, where PTVT is the proportion of success counts in the TVT sling group, PKIM is the proportion of success counts in the Neomedic KIM sling group, and Δ is the conjectured inferiority margin. We will use the chi-squared test to test the above hypothesis. In addition, we will provide the 95% confidence interval of PTVT – PKIM.

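### Surgeons know TVT Exact but may be new to KIM, and surgeon and case order are not built into randomisation, data collection or analysis, so any learning effect would be mixed into the device comparison

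*Combined protocol and SAP*

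**What the plan says.** **Experience.** Background / Rationale: "Currently in our practice we use the Gynecare TVT Exact sling, which meets these requirements". Study Intervention: "These surgeons already have experience in placing Gynecare TVT Exact slings, as this is the current standard of care".

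**Preparation for KIM.** Study Intervention: "The KIM sling has subtle differences in placement which will be addressed at the training", and "All surgeons in the study will undergo one training together prior to the start of the study". The same sentence adds individual help from device representatives. Of the training as a whole it says: "This includes but is not limited to teaching or device representatives in the operating room for intraoperative questions". No lead-in cases, minimum KIM case number, proficiency check or prior KIM experience is stated.

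**Randomisation.** Randomization, Concealment, and Blinding: "The randomization schema will be created using Stata, and this schema will be uploaded into the REDCap database". Allocation takes place in the operating room. Neither strata nor blocks are mentioned. Under Masking, "the providers in the operating room placing the sling will not be able to be blinded".

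**Data.** The baseline and concurrent-surgery variables under Outcome measures do not include the operating surgeon or the order of cases.

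**Analysis.** Plans for Aim 1 sets out a 2-by-2 table of success counts: "We will use the chi-squared test to test the above hypothesis", with a 95% confidence interval for the difference. Plans for Aims 2 repeats this at 1 year and compares complications with two-sided chi-squared tests. No analysis has a surgeon or case-order term.

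**Sample size.** Sample Size Rationale takes 90% success in both arms, a 14-point margin, a one-sided 95% limit and 80% power: 114 evaluable, 144 enrolled.

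**The concern.** The aims concern the sling, but on the text as it stands the arms may differ in two further ways: how often the operator has placed the assigned device, and whether a representative is on hand. Randomising patients does not remove a difference that comes with the device itself.

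If some KIM failures, retentions or reoperations come from unfamiliarity, they count against KIM in the pooled tables. A sling that is non-inferior once learned could then miss the 14-point test, or an early-case excess of complications could be taken for a device safety signal. Representative support described only for KIM could offset this, or push the other way. Without surgeon and case order in the plan, no pre-specified analysis could throw light on either.

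**Working it through.** **1. The plan's own figure.** Inputs from Sample Size Rationale: success 0.90 in both arms, margin 0.14, one-sided 5% (z = 1.645), power 80% (z = 0.842). The 1:1 ratio is assumed, since none is stated.

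n per arm = (1.645 + 0.842)² × (0.90×0.10 + 0.90×0.10) / 0.14² = 6.18 × 0.18 / 0.0196 = 56.8, so 57 per arm and 114 in total. With 20% dropout, 114 / 0.80 = 142.5, so 143, or 144 as two arms of 72. Both stated figures reproduce. The calculation has no allowance for a learning deficit.

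**2. Effect of a deficit in early KIM cases.** Let f be the share of KIM cases in the learning phase and l the loss of success in those cases. The average KIM shortfall is d = f × l, and

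power = Φ[(0.14 − d)/SE − 1.645], with SE = √{[0.90×0.10 + (0.90 − d)(0.10 + d)]/57}.

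The number of surgeons, the length of the learning phase and l are not in the documents. The rows below assume 3 early KIM cases per surgeon out of 72 KIM patients.

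| Surgeons (assumed) | f | l (points, assumed) | d (points) | Power |
|---|---|---|---|---|
| any | any | 0 | 0 | 80% |
| 3 | 9/72 = 12.5% | 2 | 0.25 | 78.5% |
| 5 | 15/72 = 20.8% | 2 | 0.42 | 77% |
| 3 | 12.5% | 5 | 0.63 | 76% |
| 3 | 12.5% | 10 | 1.25 | 71% |
| 6 | 18/72 = 25% | 10 | 2.5 | 62% |
| 5 | 20.8% | 15 | 3.1 | 57% |
| 8 | 24/72 = 33.3% | 15 | 5.0 | 43% |

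Worked row (5 surgeons, 15 points): d = 0.208 × 0.15 = 0.031; KIM success 0.869; SE = √[(0.090 + 0.869×0.131)/57] = 0.060; (0.14 − 0.031)/0.060 − 1.645 = 0.17; Φ(0.17) = 0.57.

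**3. How much of the KIM arm could be early cases.** If 3 to 8 surgeons share 57 evaluable KIM patients equally, each places 57/8 ≈ 7 to 57/3 = 19. Each surgeon's first five would be 15/57 = 26% to 40/57 = 70% of the arm. So f need not be small if learning takes longer than three cases.

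**4. What a case-order sensitivity analysis can show.** Drop each surgeon's first 6 randomised participants, whichever arm they are in. With 5 surgeons that removes 30 of 144 and leaves 57 per arm, or 57 × 0.80 ≈ 45 evaluable per arm. Power at 90% in both arms is then about 72%. The difference between the early and late treatment contrasts (about 12 and 45 evaluable per arm) has SE = √[(0.09 + q)(1/12 + 1/45)], where q is the KIM variance: 14 points if KIM success is 90% (q = 0.09), 17 points if it is 76% (q = 0.18). Such an analysis can describe a pattern but cannot establish learning.

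**The case against.** A reader might infer that every surgeon's first KIM placements are certain to be trial cases. The documents do not say so. They give current practice and one joint training, do not exclude earlier KIM use, and describe the training in open-ended terms. A lead-in is unstated, not ruled out.

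The protocol calls the placement differences subtle, both devices are retropubic midurethral slings, and nothing in the documents shows a learning deficit. That stands, and it is why the mild rows belong in the table.

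A reader might also fear a false non-inferiority claim. A learning deficit lowers KIM success, so it cannot produce one. The SAP's general strategies also have non-significant tests reported as inconclusive, so a failed test would not be reported as proof that KIM is inferior. The cost is a wasted answer, not a wrong claim of efficacy.

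Nor is the lack of surgeon strata a source of bias. Under concealed randomisation, chance imbalance of surgeons is random error that the interval covers. Stratifying improves precision; it does not remove learning, because each surgeon's experience with the two devices may still differ.

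Finally, it would go too far to say that device and learning could never be separated afterwards. The listed variables are those that describe the study population, not the whole dataset, and randomisation in REDCap may leave a recoverable order. What remains is that none of this is planned, while the SAP undertakes to finalise its analyses before data collection.

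**Conclusion.** The point holds as a cheap improvement to the design, not as an error in the plan's arithmetic. As written, the contrast is device plus whatever difference in operator familiarity and support comes with it, and no planned stratum, variable or analysis addresses that. Any learning deficit would act against KIM.

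The size cannot be fixed from the documents. Over assumed average shortfalls of about 0.3 to 5 points, power at 57 per arm falls from the planned 80% to between about 79% and 43%; with no shortfall the plan loses nothing. These figures rest on a 1:1 ratio, equal true success once KIM is learned, and assumed values for the number of surgeons and for the length and depth of learning.

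**What to change.** 1. Stratify the Stata/REDCap schema by surgeon, with small permuted blocks of concealed, varying size; pool low-volume surgeons into one stratum.
2. Record the operating surgeon, the within-surgeon randomisation order and each surgeon's KIM case count before the trial.
3. Pre-specify the primary risk difference and its confidence interval stratified by surgeon. State that this is for precision and does not itself remove learning.
4. Pre-specify one supportive sensitivity analysis that drops each surgeon's first few randomised participants (for example 6) from both arms. Cutting by order in both arms keeps the comparison randomised; dropping early KIM cases alone would not. Report it descriptively.
5. State that the primary conclusion stands whatever the sensitivity analysis shows, and that its result may be called compatible or not compatible with learning, no more. A rule that reads a failed primary result as a learning effect would only ever excuse KIM, and with a standard error of 14 to 17 points on the early-late contrast it could relabel a real device deficit.

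Cost: a change to the randomisation file before upload, a few REDCap fields and one extra table, with no added patients, staff or procedures. The sensitivity analysis is less precise than the primary, and strata may be small if there are many surgeons.

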Plans for Aims 2:

We will perform a similar analysis for Aim 1 to compare effectiveness at 1 year.

To evaluate the complication rates of the retropubic KIM sling compared to the TVT Exact at 6 weeks and 1 year post-operatively, we will also present 2-by-2 contingency tables on complication counts (for urinary retention, mesh exposure and reoperation for mesh complications and urinary retention). We will perform a two-sided test on comparing the proportions of complications between KIM sling and TVT Exact sling groups. Again, such a test will be performed by using the chisquared test. In addition, we will provide the 95% confidence interval of the differences of the proportions between these two groups.

Sample Size Rationale

Our statistical power calculation was based on prior studies showing retropubic sling success rate being 89-95%¹⁻⁵ and using 12-15% non-inferiority margin⁶⁻⁹. We based our sample size estimate on the following: 90% sling success with a 14% non-inferiority margin and 80% power, assuming a 20% dropout rate. If there is truly no difference between the standard and experimental treatment (90% in both groups), then 114 patients are required to be 80% sure that the upper limit of a one-sided 95% confidence interval (or equivalently a 90% two-sided confidence interval) will exclude a difference in favor of the standard group of more than 14%. To assume a 20% dropout rate, we needed to enroll 144 participants for our primary outcome of treatment success at 6 weeks postoperatively. Sample size calculator used was https://www.sealedenvelope.com/power/binary-noninferior/.

Recruitment Strategy

Once a patient has been seen by a Urogynecology physician and plans to have sling surgery for SUI, the physician will notify the study team to screen for eligibility. After the study team determines eligibility, the patient will then be approached by the study team for recruitment.

Retention Strategy

The 6 week, 6 month and 1 year visits will be incentivized monetarily in order to enhance retention. Subjects will receive \$25 with completion of the 6 week visit and \$75 with completion of the 1 year visit. The 6 month visit will be performed over the phone and/or with REDCap surveys in order to reduce the burden on the participant.

Screen Failures

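### For the two one-sided non-inferiority tests, the rule that every non-significant test is reported as inconclusive can contradict the plan's own confidence interval when KIM is clearly worse (minor)

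*Combined protocol and SAP*

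**What the plan says.** Three parts of the Statistical Analysis Plan bear on this.

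- **Strategies that Apply to all the Specific Aims**, on tests: "All hypothesis tests yielding p-values that are deemed to be not statistically significant will be reported as being inconclusive". The same bullet adds that "no p-value can reveal the plausibility, presence, truth, or importance of an association or effect".
- **The same list**, on estimates: "the analyses will focus on the magnitude and direction of point- and interval-estimates of the population parameters of interest", and "The CI will be interpreted as the set of potential values of the population parameter that are most compatible with the observed data".
- **Plans for Aim 1 and Aims 2.** For Aim 1, "we will perform the one-sided hypothesis test of" a null hypothesis that PTVT − PKIM exceeds Δ. Then: "In addition, we will provide the 95% confidence interval of PTVT – PKIM". For the later time point: "We will perform a similar analysis for Aim 1 to compare effectiveness at 1 year". A two-sided test is planned only for complications.

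The Sample Size Rationale sets the margin at 14 points and works with a one-sided 95% limit, equivalently a two-sided 90% interval. No section says how a confidence interval lying wholly above 0, or wholly above the margin, is to be described.

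**The concern.** The inconclusive label suits a two-sided test of difference, where a large p-value means that the data do not settle the direction. In a one-sided non-inferiority test a large p-value can arise in two quite different ways. The estimate may be imprecise, or KIM may have done so badly that the data lie far on the null side. The rule gives both the same word.

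The trial is meant to support using KIM in place of the sling now used in the practice. If KIM had clearly lower success, the prescribed verdict would read as though the question were still open, while the interval printed beside it said otherwise. The wording would then have to be settled after an unfavourable result was known, although the plan intends its analyses to be final before data collection.

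**Working it through.** **Inputs.** From the Sample Size Rationale: 90% success in both arms, margin 14 points, one-sided 5%, power 80%, 114 evaluable, 144 enrolled. Assumed: 1:1 allocation (the ratio is not stated), Δ in Aim 1 equal to 14 points, and the 95% CI in Aim 1 read as two-sided.

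**1. The plan's own figure.** Per arm, n = (1.645 + 0.842)² × 2 × 0.90 × 0.10 / 0.14² = 56.8, so 57 per arm and 114 in total. For dropout, 57/0.8 = 71.25, so 72 per arm and 144 in total. Both stated figures reproduce.

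**2. One result worked through: TVT Exact 52/57, KIM 34/57.**

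- Difference: 0.9123 − 0.5965 = 0.3158, or 31.6 points.
- Standard error (unpooled): √(0.9123 × 0.0877/57 + 0.5965 × 0.4035/57) = 0.0750.
- Non-inferiority test: z = (0.3158 − 0.14)/0.0750 = 2.34. The one-sided p-value is Φ(2.34) = 0.99, not significant.
- Wilson 95% limits: TVT Exact 0.8106 to 0.9619, KIM 0.4670 to 0.7138.
- Newcombe lower limit: 0.3158 − √((0.9123 − 0.8106)² + (0.7138 − 0.5965)²) = 0.3158 − 0.1553 = 0.1605, or 16.0 points without intermediate rounding.
- Newcombe upper limit: 0.3158 + √((0.9619 − 0.9123)² + (0.5965 − 0.4670)²) = 0.4545, or 45.5 points.

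Every value in the interval exceeds 14 points, yet the prescribed label is inconclusive.

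**3. Two contrasting results.** With 52/57 against 40/57 the difference is 21.1 points, Newcombe 95% CI 6.6 to 34.8, p = 0.84. KIM is worse, but the interval spans 14 points, so whether the deficit exceeds the margin is unresolved. With 51/57 against 48/57 the difference is 5.3 points, Wald 95% CI −7.1 to 17.6, p = 0.083. Here inconclusive is the right word. All three results get the same label.

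**4. How often it would matter.** All 58 × 58 outcome pairs at 57 per arm were enumerated with exact binomial probabilities and Newcombe intervals, with TVT Exact truly at 90%. Non-inferiority counts as not shown when the upper limit of the two-sided 90% interval is 14 points or more.

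| True KIM success | Non-inferiority not shown | Not shown, and 95% CI wholly above 0 | 95% CI wholly above 14 points |
|---|---|---|---|
| 76% | 95% | 51% | 2% |
| 70% | 99% | 78% | 11% |
| 65% | 99.9% | 91% | 29% |

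The last column is a subset of the one before it. At 76%, 51% − 2% leaves about 49% of trials in which KIM is shown to be worse but the interval still includes deficits smaller than the margin. If KIM is truly 90%, as the plan assumes, the third column is about 2%; at 80% it is about 30%. Wald intervals give similar figures for that column: 54% at 76% and 80% at 70%.

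**The case against.** A reader might infer that the trial could never report inferiority, or that a clear deficit could not be told apart from an imprecise result. The documents do not support either reading. The estimation bullet makes magnitude and direction the focus, the test bullet itself disclaims what a p-value can reveal, and Aim 1 supplies both the 2-by-2 table and the 95% CI of the difference. An interval of 16.0 to 45.5 looks nothing like one of −7.1 to 17.6.

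It is also fair to say that the rule is sound as a statement about the test alone. Failure to reject the null of a non-inferiority test does not establish inferiority, and the rule guards against that misreading. The percentages need the same care. The 51%, 78% and 91% count intervals above 0, not above the margin, and at a true KIM success of 76% some 95% − 51% = 44% of trials fail with an interval that includes 0, where inconclusive is correct. None of the percentages is a probability that a deficit is concealed.

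All of that stands, and it limits the point to one of labelling. It does not remove it. The rule covers all hypothesis tests without exception, it is the only verdict the plan prescribes when non-inferiority is not shown, and the emphasis on estimates does not say what to conclude when the interval and the prescribed word disagree.

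**Conclusion.** The point holds as a minor inconsistency. For the non-inferiority comparisons at 6 weeks and 1 year, a stated rule assigns the word inconclusive to results that the plan's own interval settles against KIM. The clearest cases, with the whole interval beyond the margin, arise in about 2%, 11% and 29% of trials at true KIM success of 76%, 70% and 65%. The wider group, with non-inferiority not shown and KIM worse than TVT Exact, arises in about 51%, 78% and 91%. If the two slings perform alike, as the plan expects, the conflict is rare.

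These figures rest on 57 evaluable per arm, TVT Exact at 90%, a 14-point margin and Newcombe intervals. They would shift at 1 year if fewer women were evaluable. The estimates themselves, alpha, power and sample size are unaffected.

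**What to change.** Exempt the 6-week and 1-year non-inferiority comparisons from the general rule, and prespecify the conclusion from the confidence interval for PTVT − PKIM. Name the limit used at each step, because Aim 1 promises a 95% interval while the sample-size text uses a two-sided 90% one:

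1. One-sided 95% upper limit (two-sided 90% interval) below 14 points: non-inferior.
2. Step 1 not met, two-sided 95% lower limit above 14 points: inferior beyond the margin.
3. Step 1 not met, two-sided 95% lower limit above 0 but not above 14 points: non-inferiority not shown, and KIM statistically worse than TVT Exact.
4. Step 1 not met, two-sided 95% interval includes 0: inconclusive.

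State the method used to calculate the intervals, and keep the existing wording for the two-sided complication tests.

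The cost is one SAP paragraph. It needs no extra patients or data. The only downside is that an unfavourable result would carry a less favourable label.

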- Response of "No" on UDI-6 (subscale of PFDI-20), question #3 OR if answered "yes", must indicate "no bother"
- No re-treatment with a pessary, other incontinence device or repeat surgery (urethral bulking, Burch urethropexy, sling, or other procedure)

Secondary outcomes:

- 1. SUI treatment success at 1 year
 - a. Uses same composite outcome criteria as primary outcome
- 2. Complication rates at 1 year
 - a. Urinary retention
 - b. Mesh exposure- determined by physical exam at 1 year
 - c. Reoperation for urinary retention or mesh complications thru 1 year

Baseline characteristics will be used to define the study population. Variables to be collected:

- Age- number
- Race- Caucasian/ Black/ American Indian or Alaskan Native/ Asian/ Pacific Islander/ Other
- Ethnicity- Hispanic/ non-Hispanic
- BMI- number
- POP-Q points- number

- Smoking status- non-smoker/ current/ former
- Past medical history
 - Diabetes- yes/no
 - Charlson comorbidity index- number
- Past surgical history
 - Prior hysterectomy- yes/no
 - Prior prolapse surgery- yes/no
 - Prior surgery for SUI- yes/no
 - Prior bladder tack surgery- yes/no

Data of concurrent surgical treatment at the time of intervention, which will be used to define the study population:

- Hysterectomy
- Anterior repair
- Posterior repair
- Apical suspension
 - Uterosacral ligament suspension
 - Sacrospinous ligament fixation
 - Sacrocolpopexy

Study Intervention

The KIM sling is a tension-free Knotless Incontinence Mesh (KIM) sling. Any patient with female stress urinary incontinence can be a candidate for this sling. The KIM system provides support under the urethra to decrease stress urinary incontinence in patients, similar to other slings. As opposed to other slings on the market, KIM-specific benefits include being knotless which could decrease the friction between the permanent product and patient tissue which could decrease the risk of erosion or bacteria. The sling is placed via a short, outpatient procedure where a small vaginal incision is made with two exit points through the skin. Patients can be discharged on the same day of surgery. Of note, the KIM sling also allows for a reusable trocar system.⁸

Study participants will be randomized to receive the Gynecare TVT Exact sling or the Neomedic KIM sling in the operating room by a trained Urogynecologist.

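### Does the complication comparison need a named interval method and a rule for zero events?

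*Combined protocol and SAP*

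**What the plan says.** Complications are a secondary outcome, listed under Outcome measures as "Complication rates at 1 year". They comprise urinary retention, mesh exposure, and reoperation for retention or mesh problems.

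Plans for Aims 2 covers 6 weeks and 1 year. After the 2-by-2 tables it says: "We will perform a two-sided test on comparing the proportions of complications between KIM sling and TVT Exact sling groups". It adds: "Again, such a test will be performed by using the chisquared test". It then promises that "we will provide the 95% confidence interval of the differences of the proportions between these two groups".

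The general strategies give intervals a leading role: "For each specific aim, the analyses will focus on the magnitude and direction of point- and interval-estimates of the population parameters of interest". The same list has the analysis plans finalised before data are collected, and has non-significant tests reported as inconclusive.

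No section names an interval method, says whether the chi-squared test is continuity-corrected, or covers empty tables. No section gives an expected complication rate.

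**The concern.** The plan puts the interval ahead of the p-value and reads it as the set of values most compatible with the data. For rare events, the method behind the interval then matters. The textbook large-sample (Wald) interval has zero width when neither arm has an event. Read literally, it would say that only exact equality fits the data, on the evidence of 57 to 72 women per arm. The chi-squared statistic is undefined for the same table.

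Borderline tables raise a second worry. With 4 events against 0, different versions of the test fall on opposite sides of 0.05, so a choice made after seeing the counts could decide whether a safety difference is declared. Safety is a stated secondary aim, and the plan says it sets out detailed steps for estimation and inference, so the omission deserves a check.

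**Working it through.** **Numbers per arm.** Sample Size Rationale assumes "90% sling success with a 14% non-inferiority margin and 80% power, assuming a 20% dropout rate", with a one-sided 95% limit. Allocation is taken as 1:1, which the documents do not state.

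- Evaluable: n = (1.645 + 0.842)² × (0.9×0.1 + 0.9×0.1) / 0.14² = 56.8, so 57 per arm and 114 in total, as stated.
- Enrolled: 57/0.8 = 71.25, so 72 per arm and 144 in total, as stated.

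The 57 is a 6-week planning figure; no evaluable number is given for 1 year. All complication rates below are assumptions.

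**Empty tables.** The Wald interval is d ± 1.96 × √[p₁(1−p₁)/n + p₂(1−p₂)/n]. At 0 versus 0 the standard error is 0 and the interval is [0, 0]. The Miettinen-Nurminen score interval is ±6.4 points (n = 57) or ±5.1 points (n = 72). With rate p in both arms, the chance of an empty table is (1−p)^(2n):

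- p = 1%: 0.99^114 = 32%; 0.99^144 = 24%.
- p = 2%: 0.98^114 = 10%; 0.98^144 = 5%.

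**Wald coverage, by full enumeration of the 2-by-2 tables.** When the true rates differ, an empty table can never cover the true difference. Coverage among the remaining tables is therefore (overall coverage) / (1 − chance of an empty table).

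| True rates | n per arm | Wald coverage | Chance of 0–0 | Coverage without 0–0 |
|---|---|---|---|---|
| 0.5% v 2% | 57 | 75.1% | 23.8% | 98.5% |
| 1% v 2% | 57 | 81.2% | 17.8% | 98.9% |
| 1% v 3% | 57 | 82.0% | 9.9% | 91.0% |
| 0.5% v 2% | 72 | 76.4% | 16.3% | 91.3% |
| 1% v 2% | 72 | 87.1% | 11.3% | 98.2% |
| 1% v 3% | 72 | 88.4% | 5.4% | 93.4% |

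At 2% v 5% Wald coverage is 93.3% (n = 57) or 94.6% (n = 72). At equal rates of 1% to 3% it is 95% to 99.7%. Rarity alone does not break the interval. The shortfall needs low and unequal rates, and much of it is the empty table.

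**The test the plan names.** The actual size of the uncorrected two-sided chi-squared test at n = 57 is 0.3% at a 1% rate, 1.7% at 2% and 4.5% at 5%. Over all rates its maximum is 5.3% (n = 57) or 5.5% (n = 72). It does not inflate false positives to any material degree.

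**4 versus 0 at n = 57.** d = 4/57 = 7.0 points and the pooled rate is 4/114 = 3.5%. Chi-squared = 0.0702² / (0.0351 × 0.9649 × 2/57) = 4.15, p = 0.042. The Wald interval is 0.4 to 13.7 points and Miettinen-Nurminen is 0.4 to 16.8, so all three agree. Yates-corrected chi-squared gives p = 0.127, Fisher p = 0.118, and the Newcombe interval (−0.6 to 16.7) includes 0. With equal rates of 1% to 3%, the chance of a 4–0 split in either direction is 2 × C(n,4) × p⁴ × (1−p)^(2n−4), which is 0.3% to 2.2% at n = 57 and 0.5% to 2.3% at n = 72.

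**Would an exact unconditional test do better?** A Barnard-type test on the pooled score statistic gives p = 0.049 at 4 v 0, in line with chi-squared. It parts from chi-squared in other borderline tables: 8 v 2 at n = 57 gives 0.0501 against 0.047, and 17 v 8 at n = 72 gives 0.055 against 0.048. In both tables the Miettinen-Nurminen lower limit is just above 0 (0.11 and 0.09 points), in line with chi-squared. Power at 1% v 8% is slightly lower: 44.1% against 44.5% (n = 57) and 54.8% against 56.0% (n = 72).

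**The case for a change.** The best case for a change is that the plan sets its own standard of detail, leans on intervals, and leaves the interval method open where methods differ most. Expected event counts of 5 per arm need a pooled rate of 5/57 = 8.8% or 5/72 = 6.9%, and nothing in the documents promises that. Low, unequal rates are also where a true safety difference would lie. Two analysts reading the word chi-squared could report p = 0.042 and p = 0.127 from the same 4–0 table. Naming the methods would take two sentences.

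Much of this stands as fact. The method is unnamed, the continuity correction is unstated, and Wald would perform poorly in the scenarios shown. Some of the under-coverage also remains without the empty tables: at 1% v 3% coverage is still 91% with 57 per arm.

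What does not follow is that the plan leads to a wrong result. It never prescribes Wald. A zero-width interval printed beside 0/57 and 0/57 is plainly degenerate, and an analyst would replace it. The 4–0 conflict comes mostly from tests the plan does not name; of those named, only the Yates question is open. Replacing chi-squared with an exact unconditional test would cost a little power and create new borderline disagreements with the score interval.

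**Conclusion.** No change follows. This is missing detail in a secondary safety comparison, of a kind that analysts fill sensibly, usually with a score-type interval and a count-only report when both arms are empty. No stated rule gives a wrong answer, and the one named method holds its error rate to about 5.5% at most.

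The plan also limits the damage a poor default could do. The 2-by-2 counts are presented, so any reader can recompute the interval. Non-significant tests are reported as inconclusive, so a sparse table would not pass as proof of equal safety. No safety margin or decision rule rests on this interval. Because the plan is to be finalised before data collection, the open details can be settled then as routine. The sample size and the primary 6-week analysis are unaffected.

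The conclusion assumes 1:1 allocation and 57 to 72 women per arm. The size of the possible harm (coverage of 75% to 88%) depends on assumed unequal rates of 0.5% to 3% and on an analyst choosing Wald. The documents establish neither.
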